Investigating Barriers for Decision Making in a Danish Breast Cancer Screening Context

Statistical Analysis Plan

NCT05444725

Unique Protocol ID: 2016-051-000001, 2563

Date: August 23, 2022

Statistical analysis plan

Introduction

Informed decision making and the use of decision aids are often recommended in breast cancer screening. However, informed decision making might be challenged by *ex ante* positive attitudes towards screening. Several studies have found high levels of enthusiasm towards screening including one of our own studies in a Danish breast cancer screening context (unpublished). Therefore, we will investigate preferences and attitudes towards breast cancer screening, invitation, and decision making among Danish women in this study. The study will be conducted by sending out an online questionnaire to women aged 44-49 in Denmark. Women will be randomized to one of three versions of the questionnaires: 1) Questionnaire with "Stage of Decision Making"-question to investigate women's decision making process regarding participation in screening (by asking whether women have made their decision about participation or not based on six different options of decision stages), 2) Questionnaire with choice framing (presentation of a choice between participation in breast cancer screening or no screening), or 3) Questionnaire with opportunity framing (only presentation of screening, no alternative) to investigate the decision making process and the impact of different framing. Next, women are asked to state their intended participation in screening on a 5-point Likert scale.

Subsequently, questionnaire data will be linked to register data on sociodemographic factors from Statistics Denmark.

The following variables are available:

- Register data: educational level, socioeconomic status (based on employment), civil status, municipality, and whether the person was immigrant, descendant (born in Denmark by foreign parents) or of Danish origin.
- Questionnaire: age, educational level, previous breast cancer, perceived risk of breast cancer, breast cancer worry, breast cancer among family/friends, previous mammogram, intended participation (and stage of decision making for one of three groups), reading health information in general, having read the leaflet about breast cancer screening (link in the invitation letter to this study), being more positive/negative about screening after having read breast cancer screening information, being more/less willing to participate after having read breast cancer screening information, indicating that screening participation is their very own decision vs. indicating that you should follow recommendations from health authorities about screening participation (two questions), indicating that they prefer to make their own decision about screening participation based on own attitudes and values and the information available vs. indicating that they prefer that health authorities recommend whether they should participate or not (two questions), and preferences for future screening invitation.

Hypothesis and aims

Main hypothesis: The majority of Danish women have made the decision about breast cancer screening participation prior to invitation and presentation of screening information. More specifically, the main hypothesis for this study is that 80% of Danish women have already made their decision when presented to the opportunity framing and 70% when presented to the choice framing.

To investigate the main hypothesis above, the following analyses will be performed, where subheadings indicate the theme addressed by the analyses:

Screening decision made prior to reading information

- Estimate prevalence of women who have made the decision to participate in breast cancer screening across randomization groups and for each of the two framings. Intended participation is answered on 5-point Likert scale and will be dichotomized as participation (two categories) and non-participation/unsure (three categories).
- Compare prevalence of women who have made the decision depending on opportunity vs. choice framing with chi-squared test.
- Crude and adjusted* logistic regression with intended participation as outcome and framing as independent categorical variable. The group receiving “Stage of decision making” is included in this analysis for comparison. Intended participation is answered on 5-point Likert scale and will be dichotomized as participation (two categories) and non-participation/unsure (three categories).
- Sensitivity analyses restricting intended participation to only one category for all analyses (only “Yes, I want to participate” and not “I think I want to participate”).

Stage of decision making

- Estimate prevalence of women in each decision stage based on “Stage of decision making”.
- Crude and adjusted* logistic regression with intended participation as outcome and “Stage of decision making” as independent continuous variable.

Aim 1: Women do not take the presented screening information into account when making their decision about participation.

To investigate aim 1, the following analyses will be performed, where subheadings indicate the theme addressed by the analyses:

Different framing

- Same analyses as for main hypothesis – does framing make a difference (and is information taken into account)?

Do women read health information

- Estimate prevalence of women who read health information in general and who have read the breast cancer screening information specifically.
- Crude and adjusted* logistic regression with participation as outcome and reading information (in general + screening related) as independent variables.

More or less positive/negative after reading information

- Estimate prevalence of women who are more or less positive/negative depending on previously intended participation and framing, respectively.

- Crude and adjusted* logistic regression with more or less positive/negative as outcome and intended participation and framing as categorical independent variables.

Dichotomization of outcome depends on results**

More or less willing to participate after reading information

- Estimate prevalence of women who are more or less willing to participate depending on previously intended participation and framing, respectively.
- Crude and adjusted* logistic regression with more/less willing as outcome and intended participation and framing as categorical independent variables.

Dichotomization of outcome depends on results**

Aim 2: Women think of the screening participation as less of an actual (individual) choice and more of something to comply with when invited.

To investigate aim 2, the following analyses will be performed:

- Estimate prevalence for each of the two statements (indicating that screening participation is their very own decision vs. indicating that you should follow recommendations from health authorities about screening participation) for all five categories (5-point Likert scale, "strongly agree" – "strongly disagree").
- 2x2 table of seeing it as individual choice vs. recommendation to comply with ("strongly agree" and "agree" for both statements).
- Crude and adjusted* logistic regression with thoughts on screening participation as outcome and intended participation and framing as categorical independent variables.

Thoughts on screening participation is a dichotomized variable based on the two statements mentioned above. Women are categorized as "individual choice" when they answer "agree" or "strongly agree" to the first statement and answer "neutral", "disagree", or "strongly disagree" to the other statement (coded 0). In contrast, women are categorized as "recommendation to comply with" when they answer "agree" or "strongly agree" to the second statement and answer "neutral", "disagree", or "strongly disagree" to the other statement (coded 1). Inconsistent responses to the two statements and disagreement towards both statements are coded as missing and their frequency reported.

Aim 3: Women do not want to make an informed decision about their own health (and be responsible for their own health).

To investigate aim 3, the following analyses will be performed:

- Estimate prevalence for each of the two statements (indicating that they prefer to make their own decision about screening participation based on own attitudes and values and the information available vs. indicating that they prefer that health authorities recommend whether they should participate or not) for all five categories (5-point Likert scale, "strongly agree" – "strongly disagree").
- 2x2 table of wanting informed decision making vs. health authorities make recommendation ("strongly agree" and "agree" for both statements).

- Crude and adjusted* logistic regression with preference for decision making as outcome and intended participation and framing as categorical independent variables.

Preference for decision making is a dichotomized variable based on the two statements mentioned above. Women are categorized as “wanting informed decision making” when they answer “agree” or “strongly agree” to the first statement and answer “neutral”, “disagree”, or “strongly disagree” to the other statement (coded 0). In contrast, women are categorized as “health authorities make recommendation” when they answer “agree” or “strongly agree” to the second statement and answer “neutral”, “disagree”, or “strongly disagree” to the other statement (coded 1). Inconsistent responses to the two statements and disagreement towards both statements are coded as missing and their frequency reported.

At the very end of the questionnaire, women are asked about their preferences for future screening invitation (how and what material is sent at invitation regarding invitation letter, information leaflet and pre-scheduled time for screening). For this question, four pre-defined options are suggested based on the current Danish invitation strategy and, lastly, a text field is provided for other suggestions and thoughts. Based on these responses, prevalences can be estimated for the four pre-defined invitation strategies. Next, responses provided in the text field can be investigated and possible themes and other strategies can be identified. This can be important knowledge for future research and administration of the Danish breast cancer screening program.

* The following variables are used as independent variables in adjusted analyses: educational level, socioeconomic status (based on employment), civil status, whether the person was immigrant, descendant (born in Denmark by foreign parents) or of Danish origin, perceived risk of breast cancer, breast cancer worry, and previous mammogram.

** Because women are generally very positive about screening and want to participate in screening, we hypothesize that it is more likely that women will be more negative and less willing to participate after reading screening information than becoming even more positive and more willing. This is because we assume that it is difficult to be much more positive and more willing to participate than is already the case.

If this hypothesis is true, the responses will be dichotomized as follows:

Positive/negative: Focus is on women being more negative, therefore, the two “negative” responses will be coded as 1 and the two “positive” responses and “unchanged” will be coded as 0.

More/less willing: Focus is on women being less willing to participate, therefore, the two “less willing” responses will be coded as 1 and the two “more willing” responses and “unchanged” will be coded as 0.

If our hypothesis is not true, the dichotomization will be reversed (“unchanged” will still be coded 0).

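### The main hypothesis is about prevalence levels in Danish women, but the listed analyses give plain proportions among online respondents and use the linked register data only for regression adjustment

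*SAP*

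**What the plan says.** **Target.** Under Hypothesis and aims, the SAP states: "The majority of Danish women have made the decision about breast cancer screening participation prior to invitation and presentation of screening information". It then gives figures: "80% of Danish women have already made their decision when presented to the opportunity framing and 70% when presented to the choice framing". These are levels in a national population as well as a difference between two framings.

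**Data.** The Introduction says: "The study will be conducted by sending out an online questionnaire to women aged 44-49 in Denmark". Outcomes therefore exist only for women who respond.

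**Estimator.** Under the theme on decisions made before reading information, the plan is: "Estimate prevalence of women who have made the decision to participate in breast cancer screening across randomization groups and for each of the two framings". The framings are then compared: "Compare prevalence of women who have made the decision depending on opportunity vs. choice framing with chi-squared test". The next theme adds the prevalence of each decision stage. No weight, standardisation or comparison of respondents with the population appears in any listed analysis.

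**Register variables.** The Introduction says that "questionnaire data will be linked to register data on sociodemographic factors from Statistics Denmark" and lists the variables: "Register data: educational level, socioeconomic status (based on employment), civil status, municipality, and whether the person was immigrant, descendant" (and Danish origin). Their only stated use is in the footnote marked with one asterisk, after Aim 3: "The following variables are used as independent variables in adjusted analyses: educational level, socioeconomic status (based on employment), civil status", followed by origin and three questionnaire items. Municipality is listed as available but appears in no stated analysis.

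**The concern.** The target and the estimator do not match. A proportion among respondents estimates the level in all women of that age only if response is unrelated to the answer, at least after accounting for known characteristics. The plan links characteristics that could partly test and correct this, but uses them for another purpose. An adjusted odds ratio describes an association among those who answered; it does not turn a respondent prevalence into a population prevalence.

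What is at stake is how the estimated levels are read against 80%, 70% and a majority. Women who answer a questionnaire about screening may well be keener on screening than those who do not. The Introduction reports high enthusiasm for screening in earlier studies, but nothing in the SAP shows how response relates to enthusiasm.

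**Working it through.** The SAP states no response rate, sample size or population margins, so there is no planned figure to reproduce. The 80% and 70% are hypothesised values, used below as if respondents showed exactly those levels.

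**Inputs from the SAP:** hypothesised levels of 80% (opportunity) and 70% (choice); respondents aged 44-49.

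**Assumed inputs:** response rate r; gap d = prevalence in respondents minus prevalence in non-respondents; stratum shares in step 4.

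**1. Bias of a respondent prevalence as an estimate for all invited women.** Bias = (1 − r) × d.

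| r | d (points) | Bias (points) | 80% becomes | 70% becomes |
|---|---|---|---|---|
| 60% | 5 | 0.4 × 5 = 2 | 78% | 68% |
| 50% | 10 | 0.5 × 10 = 5 | 75% | 65% |
| 40% | 20 | 0.6 × 20 = 12 | 68% | 58% |

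If d were negative, the shifts would run the other way.

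**2. What would overturn the majority claim.** The 70% level falls to 50% if the bias is 20 points. At 40% response that needs d = 20 / 0.6 = 33 points; at 60% response, d = 20 / 0.4 = 50 points. Both lie outside the range in step 1.

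**3. Bounds with no assumption about non-respondents.** The level lies between r × p and r × p + (1 − r). At r = 50%, a respondent value of 80% is compatible with 40% to 90%, and 70% with 35% to 85%. At r = 70%, the bounds are 56% to 86% and 49% to 79%. These are extremes, not expected values; they show how little the respondent figure alone fixes the level.

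**4. How much weighting could recover.** Suppose one stratum is 30% of the population but 15% of respondents.

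- Prevalence 70% in that stratum and 85% elsewhere: raw 0.15 × 70 + 0.85 × 85 = 82.75%; post-stratified 0.30 × 70 + 0.70 × 85 = 80.5%; difference 2.25 points.
- Prevalence 60% and 85%: raw 0.15 × 60 + 0.85 × 85 = 81.25%; post-stratified 0.30 × 60 + 0.70 × 85 = 77.5%; difference 3.75 points.
- Prevalence 80% in both: raw and post-stratified are both 80%; difference 0.

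Weighting removes only the part of the bias that the weighting variables explain.

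**5. The framing contrast.** If the same bias b acts in each randomised group, (80 − b) − (70 − b) = 10 points whatever b is. The difference is affected only if response, or the respondent/non-respondent gap, differs by questionnaire version.

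**The case against.** The strongest reply is that this rests on silence. The SAP nowhere says that weights will not be used, and the protocol, which may describe the sampling frame and expected response, is not at hand. The linkage statement contains no error in itself. That stands as far as it goes: the point is a mismatch between target and estimator, not a false statement. But the choice of estimator for a main hypothesis belongs in an SAP, and this one lists the analyses to be performed.

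A second reply is that the remedy does not reach the main worry. If women respond because they are interested in screening, then education, employment, civil status and origin capture only part of that. Linkage is also stated for questionnaire data only, so register data on non-respondents cannot be presumed. Both are correct; they limit what weighting can achieve and are the reason to word the conclusion with care.

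A third reply is that Aims 1 to 3 speak of women generally and also rely on regressions, so they do not all depend on population levels. This too is right, and the point is confined to the main-hypothesis and stage-of-decision prevalences.

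**Conclusion.** The point holds, as an inexpensive improvement. The main hypothesis concerns levels in Danish women; the plan, as listed, delivers levels in respondents aged 44-49; and covariate adjustment does not bridge the two. Under assumed response of 60% to 40% and gaps of 5 to 20 points, the total shift is 2 to 12 points. Its true size and direction cannot be determined from the SAP.

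A reader might infer more, and the documents do not support it:

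- **That the 80% and 70% are themselves biased.** They are hypothesised values; any bias enters the estimates later set against them.
- **That confidence intervals will be too optimistic.** The SAP mentions no confidence intervals, and selection bias shifts an estimate rather than misstating the sampling error among respondents.
- **That the bias should be judged against the 10-point gap between framings.** That gap is the randomised contrast, which is largely protected; a bias in levels has to be judged against the levels.
- **That the majority claim is in danger.** If respondents showed the hypothesised values, even the 12-point shift would leave 68% and 58%.

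**What to change.** Add a prespecified sensitivity analysis:

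- Report the main-hypothesis prevalences, overall and per framing, and the stage-of-decision prevalences, post-stratified or raked to women aged 44-49 in Denmark on register education, employment-based status, civil status and origin. Show them beside the raw figures.
- Take the weighting targets from register data on all invited women, non-respondents included, if these are held; otherwise use population margins.
- State that selection on interest in screening is not removed by this weighting.
- If raw and weighted figures differ materially, word the conclusion for respondents aged 44-49 rather than for Danish women.

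The framing test and the regressions can stay as planned. The cost is one population table, a weighted re-run and somewhat lower precision for the weighted figures. Fixing this in advance also avoids choosing between raw and weighted figures once the results are known.

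### The main hypothesis concerns having decided about screening, but the framing analyses code women who intend not to participate together with the unsure, in both the main and the sensitivity coding

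*SAP*

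**What the plan says.** All places are in the SAP.

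- **Main hypothesis (Hypothesis and aims).** The general statement is "The majority of Danish women have made the decision about breast cancer screening participation prior to invitation and presentation of screening information". It is then given numbers: "80% of Danish women have already made their decision when presented to the opportunity framing and 70% when presented to the choice framing".
- **Prevalence (Screening decision made prior to reading information).** The first bullet reads "Estimate prevalence of women who have made the decision to participate in breast cancer screening across randomization groups" and fixes the coding: "Intended participation is answered on 5-point Likert scale and will be dichotomized as participation (two categories) and non-participation/unsure (three categories". The logistic regression bullet repeats this coding.
- **Test of the framing contrast (same subheading).** "Compare prevalence of women who have made the decision depending on opportunity vs. choice framing with chi-squared test". Here the outcome is called having made the decision, without the qualification that the decision is to participate.
- **Sensitivity (same subheading).** "Sensitivity analyses restricting intended participation to only one category for all analyses", namely the firm yes. Nothing is said about the three categories on the other side.
- **Stage question.** The Introduction describes it as investigating the decision process "by asking whether women have made their decision about participation or not based on six different options of decision stages". The list of questionnaire variables shows who receives it: "intended participation (and stage of decision making for one of three groups". The planned analyses are the prevalence of each stage and a logistic model with stage as a continuous variable. Which stages count as decided is not stated.

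**The concern.** A woman who has firmly decided against screening satisfies the main hypothesis as worded, because she has made her decision about participation. Under the planned coding she counts as not having decided. Positive intention and decidedness are different quantities, and the 80% and 70% are stated for the second while the framing arms are analysed for the first.

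Two results are exposed: the levels to be set against 80% and 70%, and the difference between framings. The difference matters more. According to the Introduction, the choice framing presents no screening as an alternative and the opportunity framing does not, so refusals could plausibly be more frequent under choice framing. A shift from yes to no would then be reported as fewer women having decided, although those women had decided, only differently.

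**Working it through.** **Plan's own figures.** The SAP gives 80% and 70% as hypothesised percentages, a gap of 10 points. They are not derived from anything, so there is no calculation to reproduce.

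**Notation.** Shares within a framing arm, in percent: a = firm yes, b = tentative yes, e = firm no. The remainder is unsure or tentative no. The SAP prints only the two positive labels, so e is inferred from the name of the pooled group (non-participation/unsure).

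**Three quantities.**

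- Main coding: a + b
- Sensitivity coding: a
- Decided, taken as the firm answers at either end: a + e

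Hence decided = main − b + e, and decided − sensitivity = e. Neither planned coding equals decided, except by coincidence (b = e) or when e = 0.

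**Level.** The SAP gives no category shares. I assume e = 0-5%, a low range because the footnote on dichotomisation (**) describes women as generally very positive about screening. The sensitivity percentage is then 0-5 points below the percentage decided. Because a + e ≥ a, a sensitivity result above 50% establishes a majority whatever e is.

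**Framing gap.** Write Δ for opportunity minus choice. For a coded gap equal to the SAP's 10 points:

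gap in decided = 10 − Δb + Δe

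| Assumption | Δb | Δe | Gap in decided (points) |
|---|---|---|---|
| Tentative yes and refusals equal in both arms | 0 | 0 | 10 |
| Refusals 2 points higher under choice | 0 | −2 | 8 |
| Refusals 5 points higher under choice | 0 | −5 | 5 |
| As above, and tentative yes 5 points higher under opportunity | 5 | −5 | 0 |

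**Check of the last row with full distributions** (assumed percentages, each row summing to 100):

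| Arm | Firm yes | Tentative yes | Unsure | Tentative no | Firm no | Main | Sensitivity | Decided |
|---|---|---|---|---|---|---|---|---|
| Opportunity | 70 | 10 | 15 | 5 | 0 | 80 | 70 | 70 |
| Choice | 65 | 5 | 20 | 5 | 5 | 70 | 65 | 70 |

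The main coding shows the hypothesised 10-point gap, the sensitivity coding shows 5 points, and the gap in decided women is 0. This is the extreme corner of the assumed ranges.

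**Small case.** With 78/2/18/1/1 against 68/2/28/1/1, in the same order of categories, main is 80% against 70% and decided is 79% against 69%. When tentative yes and refusals are both rare and equal, almost nothing is lost.

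**The case against.** The best defence is that the operational definition is open. The first bullet says the decision is to participate and fixes the coding at once. The chi-squared bullet follows directly and can be read as shorthand for the same percentage. The study is motivated by enthusiasm for screening, and refusals are expected to be few. This stands as far as it goes: a reader knows what will be computed. It does not remove the mismatch with the hypothesis, because no planned framing analysis separates refusals from uncertainty.

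A reader might also infer more than the SAP supports:

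- **That the framing arms measure only positive intention.** They do not. The five-point item records negative answers, and it is the dichotomisation that loses the distinction.
- **That the framing arms cannot inform the main hypothesis at all.** The firm-yes percentage is a lower bound on decided and can support the majority claim. What is exposed is the 80% and 70% levels and the gap.
- **That a coded 80% might mean anything from 60% to 85% decided.** With b at 0-20% and e at 0-5%, the arithmetic is 80 − 20 + 0 = 60 and 80 − 0 + 5 = 85. But 20 of those 25 points come from the tentative yes, which the sensitivity analysis removes. The unhandled part is e.
- **That the missing cut on the stage question is a serious gap.** Every stage will be reported and no planned test uses a cut, so any grouping can be read off. It is a secondary point.

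For Aim 1, which reuses these analyses to ask whether framing makes a difference, positive intention is a suitable outcome. A move from yes to no is a genuine framing effect there.

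**Conclusion.** The concern holds as a mismatch between the hypothesis and the coded outcome, and it should be corrected. Followed as written, the plan counts women who have decided against screening as undecided in both codings, so it can misstate the levels and the framing gap for the main hypothesis.

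The size is unknown and probably small if refusals are rare. With assumed refusals of 0-5%, the firm-yes level is 0-5 points too low. With tentative yes equal across arms and refusals 0-5 points higher under choice framing, a coded gap of 10 points corresponds to 5-10 points in decided women. The gap vanishes only if tentative yes also differs by 5 points in the unfavourable direction. It would be wrong to conclude that the framing contrast is an artefact: the SAP contains no category shares, so these figures show what is possible, not what is likely.

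The result rests on two further assumptions: that the item has a firm-no category, which the SAP does not print, and that the firm answers are a fair proxy for having decided.

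**What to change.** Choose one of two changes before analysis.

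- **(a) Add an outcome for decided women.** For the main hypothesis, code decided as the firm categories at both ends of the intention item against the rest, subject to the questionnaire's labels and acknowledged as a proxy. Use it in the prevalence, chi-squared and logistic analyses. Keep the present coding as a separate outcome named intention to participate, which also serves Aim 1.
- **(b) Restate the hypothesis.** Word the main hypothesis and its 80% and 70% as intention to participate, and stop describing the outcome in the analysis bullets as a decision already made.

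As a secondary matter under either option, name in advance which of the six stages count as decided.

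The cost is SAP wording and, under (a), one recoded variable from items already in the questionnaire. Under (a) the percentage decided may be lower or higher than the present coding would give, and it remains a proxy. Under (b) the framing arms no longer address whether women have decided, and only the stage-question group does.

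### Does Aim 1 need rewording because the framing comparison cannot by itself show whether women use the screening information?

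*SAP*

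**What the plan says.** The Introduction of the SAP describes the two framing arms. The choice arm gets "presentation of a choice between participation in breast cancer screening or no screening"; the opportunity arm gets "only presentation of screening, no alternative". A third arm gets a question on stage of decision making instead. The order is then given: "Next, women are asked to state their intended participation in screening on a 5-point Likert scale".

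The main hypothesis, under Hypothesis and aims, is that "The majority of Danish women have made the decision about breast cancer screening participation prior to invitation and presentation of screening information". It is made specific as "80% of Danish women have already made their decision when presented to the opportunity framing and 70% when presented to the choice framing". The analyses that compare the framings stand under the subheading "Screening decision made prior to reading information".

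Aim 1 holds that women leave the screening information they are shown out of their decision. Its first theme, Different framing, repeats the main-hypothesis analyses and adds the question "does framing make a difference (and is information taken into account". Three further themes follow: whether women read health information, whether their attitude changed after reading, and whether their willingness to take part changed after reading. The questionnaire variables include "having read the leaflet about breast cancer screening (link in the invitation letter to this study", so the leaflet reaches women through the letter. No version of it specific to an arm is described.

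**The concern.** The bracketed question seems to ask more of the comparison than it can give. What is randomised is the framing, not the information. If intention differs between the arms, the wording alone could be the cause. If it does not differ, women may still have read and weighed the leaflet.

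There is also a tension within the SAP. The main hypothesis predicts different shares under the two framings among women said to have decided before any information was presented. If the same difference is then read under Aim 1 as a sign that information counts, confirming the main hypothesis would speak against Aim 1. The SAP does not say which result of this theme would support the aim. At stake is a report that draws a conclusion about use of information from a contrast that cannot carry it.

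**Working it through.** No sample size, power or significance level bears on this point, so the check is mainly a comparison of statements in the SAP.

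**1. What differs between the arms.** By the Introduction, the framing arms differ in whether no screening is presented as an alternative. By the list of questionnaire variables, the leaflet is linked in the study's invitation letter, with no difference by arm described. The contrast therefore estimates the effect of naming the alternative. It does not estimate the effect of the leaflet.

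**2. When the outcome is placed.** The reused analyses are labelled as concerning decisions made before reading. In the two change-after-reading themes of Aim 1, intention is again treated as coming first, because the prevalences are broken down by it. Intention is asked after the framing, so some women could open the leaflet in between. Any effect passing through reading would be mixed with the effect of wording, and the contrast could not separate them.

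**3. The SAP's own figures.** The only framing figures are 80% (opportunity) and 70% (choice). Assume that they are shares on the analysed outcome, intended participation in two categories:

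- Difference: 0.80 − 0.70 = 0.10, or 10 percentage points.
- Odds ratio, opportunity against choice: (0.80/0.20) / (0.70/0.30) = 4.00 / 2.33 = 1.71.

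The main hypothesis expects this difference among women who decided before information was presented. A result of this size would thus not by itself indicate use of information. The odds ratio only restates the two percentages and measures no bias.

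**4. How much of Aim 1 rests on it.** The themes are:

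| Aim 1 theme | What it measures | Role of framing |
|---|---|---|
| Different framing | Stated intention | Randomised contrast |
| Reading health information | Reading, and its association with participation | None stated |
| Attitude after reading | Self-reported change | Independent variable, with intention |
| Willingness after reading | Self-reported change | Independent variable, with intention |

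One theme in four carries the bracketed question. Two of the others already relate framing to reported change after reading, which is nearer to the aim.

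**5. What a rewording would achieve.** Dropping the bracket and relabelling the theme as an effect of framing on intention leaves the data, the models and the estimates as they are. Taking the theme out of Aim 1 would leave the aim on reading and change after reading. Reading is self-selected and self-reported: an association with intention may reflect prior interest in screening, and no association does not show that the leaflet was ignored. Those analyses face the same two-sided limit as the framing contrast, and reading is not randomised.

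**The case for a change.** The best case for a change is this. The SAP lists the framing comparison among the analyses to be performed for Aim 1, so it is more than a passing remark. An outcome labelled as prior to information cannot also test whether information was used. Because the SAP does not say which result favours the aim, the interpretation could be chosen once the results are known. Removing the bracket costs only a few words.

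Most of the reasoning stands: the contrast cannot isolate use of the leaflet, and a report should not claim that it does. Three things weigh against a change to the plan.

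- The SAP never states the inference. It poses a question in brackets, attaches no criterion to it and surrounds it with analyses aimed at reading and its consequences.
- Naming the option of no screening can fairly be read as presented content that differs by randomisation. On that reading the question makes sense. The main hypothesis tells against it by placing the decision before information is presented, but the same paragraph speaks of women having already decided when shown a framing. The wording is loose in both places, and the framing texts are not in the SAP, so the matter cannot be settled from it.
- That no criterion is given for supporting Aim 1 is a separate matter. It does not show that the framing comparison was wrongly included.

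**Conclusion.** No change to the plan follows. The limit on inference is genuine but small: it affects the interpretation of one of four Aim 1 themes and no planned estimate, and no bias can be quantified. Keeping the randomised comparison beside the observational analyses is a fair trade-off, since neither kind alone can establish whether information is used. An analyst would ordinarily report the framing result as sensitivity to presentation and judge use of information across all the Aim 1 themes, noting that reading and change after reading are self-reported and not randomised.

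This conclusion assumes that the arms differ as the Introduction describes and that the leaflet is the same for all arms. It would need another look if the questionnaire texts showed that the arms carry different screening information.
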